### ***SIDE EFFECTS AND MISCELLANEOUS***

#### Magnesium variables

1. Magnesium levels
  - average daily level (for each post-operative day), average total level
  - peak level during admission
2. Dosing
  - # of magnesium infusion dosing changes (i.e. # times decreased)
  - total days on magnesium (POD# at discontinuation)
  - # times held due to adverse event concern
  - # of adverse events deemed secondary to magnesium
  - type of adverse event
3. OR Effect
  - Time spent bradycardic (value and %)
  - Overall OR time
  - Fluid requirement
  - Blood product requirement
  - Pressor variables (# required, peak doses)
4. Other effects
  - ionized calcium levels – average daily level (for each post-operative day) and average total level
  - potassium levels – average daily level (for each post-operative day) and average total level
  - phosphorous levels - average daily level (for each post-operative day) and average total level

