## MEDICAL PROTOCOL (HRP-590)

PROTOCOL TITLE: Magnesium sulfate as adjuvant analgesia and its effect on opiate use by post-operative transplant patients in the pediatric ICU.

VERSION DATE: 06/09/2022

Control Group: For collection of control data, a MRN list of the most recent 60 transplant patients under the same surgeon at this institution (30 liver, 30 TPIAT) who have not opted out of research will be obtained via UMN's Best Practices Integrated Informatics Core (BPIC), followed by access to EPIC EMR outside of the Information Exchange to review patient's chart and collect for intended outcomes, which are also uploaded into RedCap. This will be done in identical manner as that for prospective data collection — the EMR will be accessed for appropriate patient by MRN, followed by selecting the appropriate surgical encounter by date, followed by selecting only specific portals in epic where intended data elements are located (for example: Intake/Output section, or results review -> magnesium level, etc). Collection of this data will be initiated at the start of IRB approval and ongoing to completion. Full data analysis will be completed at conclusion of study followed by construction of manuscript. Of note, hypomagnesemia is corrected per standard ICU care with IV MgSO4 regardless of study, and liver transplant patients currently have a pre-designed magnesium replacement protocol (also used in our CVICU post-operative cardiac patients). This will still be included in data collection without adjustment to any comparison data in statistical analysis. This replacement protocol will not be used in our study as we will already be providing continuous IV MgSO4. Similarly, magnesium blood levels are checked independent of this study, although will be more frequent now for safety monitoring. These blood levels are drawn through a central line that is already in place independent of this study, so will not require percutaneous needle stick. There are no other drugs/devices involved in study or that would alter MgSO4 delivery.

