## 13. Risks to Participants

*13.1. Foreseeable Risks:* This would include the potential for known side effects from magnesium toxicity, namely: hypotension, cardiac arrhythmia, hyporeflexia, effects on other electrolytes (such as potassium and calcium), muscle weakness, respiratory depression (secondary to muscle weakness), and increased sedation (including when combined with opioids and benzodiazepines). These toxic risks are cited typically at levels of > 4-4.5 mg/dL. We will minimize this risk by targeting magnesium thresholds below this. Hypotension is monitored for via routine serial blood pressure monitoring in all ICU patients, and can be treated with IV fluid resuscitation as needed (standard for hypermagnesemia treatment). Cardiac arrhythmia is monitored for via cardiac telemetry in all ICU patients, and cardiology specialists and arrhythmia resuscitation techniques are available per standard ICU care. Both of these are risk factors that are present in these populations regardless of magnesium use, however if these conditions are felt potentially contributed to by hypermagnesemia the infusion will be stopped for further evaluation. Electrolyte abnormalities are also common in ICU populations and are monitored routinely per post-transplant protocols. Respiratory depression is monitored routinely in this population as well, however if secondary to perceived muscle weakness out of proportion to standard post-operative course, the magnesium infusion will be stopped as well. Sedation and other analgesia is routine in post-operative transplant care and is addressed and titrated based on daily goals. Decreasing other sedatives will take precedent over magnesium in cases of oversedation given the overall objective of the study. Increased blood draws may occur during monitoring, however in 48 hours of infusion may result in only 4-8 mL of extra blood specifically from magnesium draws alone, which clinically seems insignificant relative to overall course. There is potential for dosing error as is for all PICU delivered medications, however correct units for MgSO4 has been updated in UMMCH pump library, and there is additionally standard ICU regulations per institutional and leadership for routine drip/dose checks. The only other potential foreseeable risk would be that of intravenous line capability. Post-operative transplant patients require multiple IV

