## MEDICAL PROTOCOL (HRP-590)

PROTOCOL TITLE: Magnesium sulfate as adjuvant analgesia and its effect on opiate use by post-operative transplant patients in the pediatric ICU.

VERSION DATE: 06/09/2022

18.2. Data Safety Monitoring: The following safety data will be collected starting at the baseline visit through the end of study visit to establish any change from baseline parameters, and for monitoring adverse events:

- Confirm that participant met inclusion/exclusion criteria
- Confirm that delivered magnesium dose is appropriate with intended protocol dosing (i.e. 50 mg/kg bolus, 15 mg/kg/hr infusion)
- hypotensive events: including value and interventions needed (pressors, fluid bolus, etc)
- respiratory decline: specifically if needing to increase to higher level of support (nasal cannula to high flow, high flow to positive pressure, etc), interventions required for respiratory compromise, relation to sedation
- arrhythmia: include type, EKG results (if done), interventions required
- hypocalcemia: specifically if ionized calcium < 4 (or age-appropriate norm), interventions required
- hyperkalemia: include value (if higher than normal range), interventions required
- hyperphosphatemia: include value (if higher than normal range), interventions required
- hypermagnesemia: include if > 3.5, confirm that dose was decreased per protocol guideline
- for all of above, comment on whether side effects deemed secondary to magnesium

Safety data will be captured in the CRFs for each visit. Any AEs and SAEs will also be recorded in the REDCap database. Any safety event meeting the IRB's urgent reporting criteria will be reported to the IRB within its published timelines, and similarly to the FDA as outlined at conclusion of this section.

A pediatric ICU physician external to the research team will serve as the safety monitor for this protocol. The safety monitor will not be enrolling any research participants or caring for patients as part of this protocol. The safety monitor is qualified to review the patient safety data generated by this study because of her/his expertise in pediatric intensive care.

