## MEDICAL PROTOCOL (HRP-590)

PROTOCOL TITLE: Magnesium sulfate as adjuvant analgesia and its effect on opiate use by post-operative transplant patients in the pediatric ICU.

VERSION DATE: 06/09/2022

efficacy, the data and adverse event review will be completed after every 5 patients for duration of the study, unless any clinically relevant items deem alteration of these review intervals. Any serious or unexpected events will be thoroughly investigated followed by a short report independent of the above 3 and 5 patient review intervals. PI is responsible for notifying safety monitor via telephone or email of any events within 1 day that she or trial team are made aware.

We do not predict any adverse events to occur at our protocol dosing based on available literature. If a SAE, Unanticipated Problem Involving Risks to participants or Others (UPIRTSO) or other event causing risk to the research participants occurs, the clinical research team will notify safety monitor immediately. Safety monitor will assure the study is conducted in accordance with the investigator's agreement, the investigational plan, the IND and other applicable FDA regulations, and conditions of approval imposed by the reviewing IRB or FDA. Research will be suspended immediately if any life-threatening events occur due to magnesium.

An Annual Report will be compiled by the research team and will include a list and summary of AEs. In addition, the Annual Report will address (1) whether AE rates are consistent with pre-study assumptions; (2) reason for dropouts from the study; (3) whether all participants met entry criteria; (4) whether continuation of the study is justified on the basis that additional data are needed to accomplish the stated aims of the study; and (5) conditions whereby the study might be terminated prematurely.

The Annual Report will be sent to the safety monitor and will be forwarded to the IRB and FDA. The IRB and other applicable recipients will review progress of this study on an annual basis.

Below outlines definitions and specifics regarding relevant events:

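### Magnesium's haemodynamic toxicities have no control rate in the PICU: bradycardia, fluids and pressors are abstracted for the OR only, and PICU hypotension and arrhythmia only in the participant safety list

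*Combined protocol and SAP*

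**What the plan says.** Section 15.1, Magnesium variables, item 3 (OR Effect) lists "Time spent bradycardic (value and" percentage), "Fluid requirement" and "Pressor variables (# required, peak doses"), together with OR time and blood products. Nothing else in 15.1 records blood pressure, heart rate, rhythm, pressors or fluids after the child reaches the PICU.

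For control abstraction, section 5.2 says: "This will be done in identical manner as that for prospective data collection". The OR items should therefore exist in both cohorts, and the PICU items in neither.

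Section 18.2 asks for "hypotensive events: including value and interventions needed (pressors, fluid bolus, etc") and "arrhythmia: include type, EKG results (if done), interventions required". That list runs from a baseline visit to an end-of-study visit, is captured on CRFs, and includes confirming that the delivered magnesium dose matched the protocol.

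Section 13.1 puts hypotension and arrhythmia first among the foreseeable risks and adds: "Both of these are risk factors that are present in these populations regardless of magnesium use". Section 18.2 also requires the Annual Report to address "whether AE rates are consistent with pre-study assumptions". The only assumption stated there is that no adverse events are predicted at the protocol dosing.

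**The concern.** The protocol accepts that hypotension and arrhythmia occur in these children without magnesium, so a count in the treated cohort means little without a background rate. The 60 controls could supply that rate from charts already being read, but the data list does not ask for it.

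The gap falls on the part of the exposure that is new. Section 4.1 gives the extended infusion duration as one reason for the IND, and section 2.3 says paediatric infusions beyond 24 hours are known only from asthma studies. The two-cohort haemodynamic data stop when the child leaves the OR. The safety monitor, who looks for clinically significant trends, and the Annual Report would have no PICU haemodynamic rate from the same unit to read against.

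**Working it through.** **Where each toxicity named in 13.1 is measured in the PICU**

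| Toxicity | Both cohorts (15.1) | 18.2 safety list only |
|---|---|---|
| Hypotension | none (pressors and fluids are OR only) | yes |
| Bradycardia, arrhythmia | none (time bradycardic is OR only) | yes (arrhythmia) |
| Respiratory depression | escalations, daily peak requirement, days intubated, re-intubations | – |
| Electrolytes | daily calcium, potassium, phosphorus | – |
| Sedation | indirect: COMFORT-B, dexmedetomidine, midazolam | – |

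The adverse-event items in 15.1 (infusion held, event deemed secondary to magnesium) exist only where study magnesium was given, so they yield no background rate. The gap is haemodynamic.

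**Share of the infusion spent in the PICU**

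Input: 48 hours of infusion after the bolus (4.1). OR infusion hours are not in the documents and are assumed. Share = (48 − OR hours)/48.

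- 4 h: 44/48 = 92%
- 8 h: 40/48 = 83%
- 12 h: 36/48 = 75%
- 16 h: 32/48 = 67%
- 24 h: 24/48 = 50%

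So "most" holds for any OR infusion time under 24 hours, provided the infusion runs its full course. It can fail in a child titrated off early: three reductions of 5 mg/kg/hr take 15 mg/kg/hr to zero, and levels are drawn every 2 hours in the OR.

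**What treated-only counts give (exact 95% CI, n = 30)**

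- 0/30: upper limit 1 − 0.025^(1/30) = 11.6%.
- 6/30 = 20%: 7.7% to 38.6%.

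Neither count has a control rate beside it.

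**What a 30 against 60 comparison would give**

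Cohort sizes are from 16.4. Control rates are not in the documents, so 10%, 20% and 30% are assumed. With equal rates p in both cohorts, half-width = 1.96 × √[p(1 − p)(1/30 + 1/60)] = 1.96 × √[p(1 − p) × 0.05].

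- p = 10%: 1.96 × √0.0045 = 13 points
- p = 20%: 1.96 × √0.0080 = 17.5 points
- p = 30%: 1.96 × √0.0105 = 20 points

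With a two-sided 5% test (normal approximation, pooled variance under the null), the treated rates detectable with 80% power are about 35%, 49% and 60%.

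Illustration with unequal rates, 40% treated against 20% control: SE = √(0.24/30 + 0.16/60) = 0.103. The difference is +20 points ± 20.2, an interval that just includes zero.

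**The plan's own figure**

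The only power figure (15.2) concerns opioid dose. It reproduces: a two-sample t-test with SD 8.3 mg/kg and 90 per group detects 3.49 mg/kg with 80% power. Nothing here depends on it.

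**The case against.** - **The comparator gap is not general.** A reader might infer that magnesium's main toxicities as a whole lack a comparator. The table shows otherwise: respiratory support and electrolytes have daily PICU data in both cohorts, and sedation has indirect measures. Only the haemodynamic effects are uncovered.
- **Section 18.2 does not exclude controls in so many words.** This is correct. That it covers treated children only is an inference from its visit, CRF and dose-check wording. Section 15.3 also compares the presence of side effects between groups, but the term is undefined and no control-side PICU haemodynamic variable stands behind it. The separate data-measures attachment is not available; 15.1 describes it as the same measures in list form.
- **Attribution does not rest on bedside opinion alone.** This is also correct. There is an external PICU physician as safety monitor, review after 3 patients and then every 5, causality grading, serial magnesium levels, and IRB and FDA review after a halt. The halt rules turn on one or two individual events, which a historical group rate would not decide. The control rate would be context only.
- **The added data would not settle whether the infusion causes hypotension.** They would not: the comparison is historical and imprecise, as the ±20 points shows. Its value is a background rate that the pilot cannot otherwise report.
- **OR focus is a reasonable pilot choice.** The bolus is given there, and its timing in liver recipients was set with haemodynamic risk in mind. That justifies measuring in the OR. It does not justify stopping there when the infusion continues.
- **Prospective and retrospective charting may capture events differently.** This stands, and it affects the choice of measures in the fix.

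**Conclusion.** The concern holds in a limited form. As written, the plan yields no control rate for PICU hypotension, bradycardia, arrhythmia, pressor use or fluid boluses. For a full 48-hour infusion this leaves about 67% to 92% of the infusion without a two-cohort haemodynamic measure, if 4 to 16 hours fall in the OR. The conclusion rests on three points: OR infusion time under 24 hours, the reading of 18.2 as covering treated children only, and the unavailable attachment matching 15.1.

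The documents do not support going further, to say that respiratory or electrolyte safety is uncompared, that safety oversight is missing, or that the pilot would become able to establish a haemodynamic effect once the data are added. This is a worthwhile, inexpensive improvement to a pilot's safety description, and does not affect the primary analysis.

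**What to change.** **Section 15.1.** Add for both cohorts, from the same EMR sources and with identical written definitions:

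- PICU pressor use (number, peak dose)
- fluid boluses
- hypotension needing intervention
- time bradycardic
- arrhythmia needing intervention

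Make pressor and fluid-bolus records the main measures, because they depend least on how closely someone was watching. Intervention-based definitions also avoid the non-sustained hypotension that the section 18 adverse-event text says will not be reported individually.

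**Window.** Align it with the exposure, for example from PICU arrival to 48 hours after the end of the OR bolus. Counting 48 hours from PICU arrival would run past the end of an infusion begun in the OR. Give controls an equivalent surgical time anchor by transplant type, such as induction for TPIAT and reperfusion for liver, allowing for the 30-minute bolus. Keep the window the same whether or not magnesium was stopped early, in line with the intention-to-treat rule in 15.3.

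**Section 15.3.** Report each group difference adjusted for transplant type with a 95% CI, labelled descriptive. State in 18.2 whether its list applies to controls, and define the side effects compared in 15.3.

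**Safety monitor.** Supply the control rates as background context. The halt rules stay as they are.

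**Cost.** More abstraction from charts already under review for 90 patients, an update to the approved data list (control review is under a consent waiver and limited to specified chart areas), and a hypotension definition that works across ages 3 to 17. Some differential ascertainment will remain and should be stated as a limitation. There is no patient contact and no change in sample size.

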## MEDICAL PROTOCOL (HRP-590)

PROTOCOL TITLE: Magnesium sulfate as adjuvant analgesia and its effect on opiate use by post-operative transplant patients in the pediatric ICU.

VERSION DATE: 06/09/2022

- PTH level (for renal patients where relevant)
- creatinine levels (average daily and average total; part of routine monitoring of all transplant patients)

### Standard Reporting

2. type of transplant received
3. age
4. weight
5. height
6. gender

*15.2. Power Analysis:* Power analysis was performed based on pediatric studies by Hutchins et al and Jabbour et al (see references section 24), indicating 90 patients in order to see a detectable difference of 20% between study groups with 80% power. This would detect a decrease of nearly 3.5 mg/kg over a 7 day PICU course, and seemed a reasonable target for our hypothesis. Given the progression of IND review, this number will be reduced to 60 for the retrospective cohort (renal transplants removed from study), and 30 for prospective cohort (typical target for pilot-based study), to simulate a pilot study rather than fully correlational study. Regardless, original power analysis is shown below:

n per group	Detectable difference between groups (Total 1st 7 days in morphine equivalent mg/kg)		Detectable difference between groups (% reduction in dose)	
	80% power	90% power	80% power	90% power
40	5.26	6.09	29	33
50	4.70	5.43	26	30
60	4.28	4.95	24	28
70	3.96	4.58	23	26
80	3.70	4.28	21	24
90	3.49	4.03	20	23
100	3.30	3.82	19	22
110	3.15	3.64	18	21
120	3.01	3.49	18	20

Based on a pooled SD estimate for total morphine equivalent dose first 7 days post-op of 8.3 mg/kg (Hutchins 2016), the table lists the minimum differences (in mg/kg) that are detectable with 80% and 90% power for various enrollment sizes. These differences are also presented in terms of the % reduction in total dose, based on an overall mean total dose of 15.5 mg/kg (Hutchins 2016). For comparison, a 29.5% reduction in total dose (first 48h) in ketamine + magnesium versus ketamine was observed in Jabbour 2014.

*15.3. Statistical Analysis:* The primary analysis will compare the total morphine equivalent dose per kg during the PICU stay between experimental and historical control groups. Total dose will be compared in both unadjusted analyses and adjusted analyses using linear models, with a covariate for study group and adjusting covariates for transplant type, age, and gender, to account for potential variation due to these factors. Distributional assumptions will be examined and data transformations will be used as appropriate. Secondary outcomes will be compared using similar approaches using generalized linear models for count

## MEDICAL PROTOCOL (HRP-590)

PROTOCOL TITLE: Magnesium sulfate as adjuvant analgesia and its effect on opiate use by post-operative transplant patients in the pediatric ICU.

VERSION DATE: 06/09/2022

outcomes (total days on IV opioids, number of PCA demands and deliveries, number of infusion dose escalations, number of ileus events, days until first stool, emesis counts, number of days naloxone infusion required, PICU duration, number of days intubated, paravertebral block dose increases), categorical outcomes (ketamine use, presence of side effects), and continuous outcomes (FLACC, Pain Score). Longitudinal measurements of magnesium, other analgesics, ionized calcium, PTH, and creatinine levels will be analyzed using mixed effects models. Group summaries including means, standard deviations, and rates will be reported and group differences will be summarized as incidence rate ratios, odds ratios, or mean differences with 95% confidence intervals. Analyses will be conducted using the intent-to-treat principle; control group participants who underwent magnesium replacement (for hypomagnesemia or pre-designed post-transplant protocol) will be included in the control group, and experimental group participants with discontinuation of magnesium, if any, will be included in the experimental group. A two-sided 5% level result will be regarded as significant. Statistical analysis will be per statistician's updated STATISTICAL ANALYSIS SOFTWARE (also used in a previous pain study with TPIAT cohort).

### *15.4. Data Integrity:*

Data collection is the responsibility of the clinical study staff at the site under the supervision of the site PI. The investigator is responsible for ensuring the accuracy, completeness, legibility, and timeliness of the data reported.

Source data are all information, original records of clinical findings, observations, or other activities in a clinical trial necessary for the reconstruction and evaluation of the study. All paper data (which would include only consent/assent forms) will be kept in a dedicated, locked, research space, in co-investigator's office at UMN Children's Hospital. Other source data will be stored in EPIC. Consent and assent forms will be transitioned to the patient chart upon completion. Paper copies of these forms will be stored in a locked storage bin in co-investigator's office at UMN Children's Hospital.

Protocol with study schedule and patient enrollment will be tracked with OnCore programming. Electronic data collected from the PICU admission will be stored on REDCap program as a clinical database, a secure environment delivered by the Center of Excellence for HIPAA Data intended for storing, sharing and accessing sensitive and private highly restricted files.

Data access will be limited to research assistant, research coordinator, statistician support, and key study personnel (PI and co-investigators).

Upon completion of project, the master data matrix and patient identification key will be destroyed.

